6.11 Active Treatment Extension

Participants who have completed the placebo-controlled portion of the trial will be eligible to continue in the ATE as outlined in the SOA.

Modifications to ATE Regimen Schedule

Designated visits in the SOA (i.e., ATE Week 4, ATE Week 8, ATE Week 16, ATE Week 28, ATE Week 40) may be conducted via telemedicine (or phone if telemedicine is not available) with remote services instead of in-person if needed to protect the safety of the participant due to a pandemic, disability, or other medically necessary reason. If an in-clinic visit is conducted remotely for disability or a medically necessary reason, the next scheduled in-clinic visit must occur in-person unless otherwise approved by the Medical Monitor.

In addition to the procedures in the Master Protocol that should be conducted during the phone or telemedicine and remote visits, the following regimen-specific procedures should be completed:

- ALSAQ-40 (as scheduled at ATE Week 28)
- ROADS (as scheduled at ATE Week 28)
- Menstrual cycle questionnaire for women of child-bearing potential

Details on performing assessments and dispensing IP during remote visits are described in the MOP.

6.11.1 ATE Week 2 Telephone Visit

This visit will take place via telephone 14 ± 3 days after the Week 24 Visit of the placebocontrolled portion of the trial. The following procedures will be performed:

- Review concomitant medications
- Assess and document AEs, including Key Study Events (see section 10.3 of Master Protocol)
- Perform IP compliance (remind of the importance of compliance)
- Remind participant to bring any unused IP to the next visit

6.11.2 ATE Week 4 Visit

Participants should be instructed to hold IP on the day of the study visit. Investigational product should not be taken until after study visit procedures are complete.

This visit will take place in-person 28 ± 7 days after the Week 24 Visit of the placebo-controlled portion of the trial. The following procedures will be performed:

- Collect vital signs including weight
- Perform SVC
- Administer ALSFRS-R questionnaire
- Review concomitant medications

- Assess and document AEs, including Key Study Events (see section 10.3 of Master Protocol)
- Administer the C-SSRS Since Last Visit questionnaire
- Collection of blood samples [pre-dose]
 - Collect blood samples for Clinical Safety Labs and, for WOCBP, for pregnancy test if applicable
 - Hormone safety laboratory tests
- Menstrual cycle questionnaire (for women of child-bearing potential)
- Perform IP compliance (remind of the importance of compliance, count number of unused sachets remaining in participant's supply from the previous clinic visit)
- Remind participant to bring any unused IP to the next visit

6.11.3 ATE Week 8 Visit

Participants should be instructed to hold IP on the day of the study visit. Investigational product should not be taken until after study visit procedures are complete.

This visit will take place in-person at 56 ± 7 days after the Week 24 Visit of the placebocontrolled portion of the trial. The following procedures will be performed:

- Collect vital signs including weight
- Perform SVC
- Muscle strength assessment
- Administer ALSFRS-R questionnaire
- CNS Bulbar Function Scale
- Review concomitant medications
- Assess and document AEs, including Key Study Events (see section 10.3 of Master Protocol)
- Administer the C-SSRS Since Last Visit questionnaire
- Collection of blood and urine samples [pre-dose]
 - Collect blood samples for Clinical Safety Labs and, for WOCBP, for pregnancy test if applicable
 - Plasma/serum for biomarker analyses
 - Collect urine for biomarker analyses
 - Collect blood RNA
- Menstrual cycle questionnaire (for women of child-bearing potential)
- 12-Lead ECG
- Dispense IP to participant
- Perform IP compliance (remind of the importance of compliance, count number of unused sachets remaining in participant's supply from the previous clinic visit)
- Remind participant to bring any unused IP to the next visit

6.11.4 ATE Week 12 Telephone Visit

This visit will take place via telephone at 84 ± 3 days after the Week 24 Visit of the placebocontrolled portion of the trial. The following procedures will be performed:

- Administer ALSFRS-R questionnaire
- Review concomitant medications
- Assess and document AEs, including Key Study Events (see section 10.3 of Master Protocol)
- Perform IP compliance (remind of the importance of compliance)
- Remind participant to bring any unused IP to the next visit

6.11.5 ATE Week 16 Visit

Participants should be instructed to hold IP on the day of the study visit. Investigational product should not be taken until after study visit procedures are complete.

This visit will take place in-person at 112 ± 7 days after the Week 24 Visit of the placebocontrolled portion of the trial. The following procedures will be performed:

- Collect vital signs including weight
- Perform SVC
- Administer ALSFRS-R questionnaire
- CNS Bulbar Function Scale
- Review concomitant medications
- Assess and document AEs, including Key Study Events (see section 10.3 of Master Protocol)
- Administer the C-SSRS Since Last Visit questionnaire
- Collection of blood and urine samples [pre-dose]
 - Collect blood samples for Clinical Safety Labs and, for WOCBP, for pregnancy test if applicable
 - Hormone safety laboratory tests
 - Coagulation laboratory tests (if proceeding with optional CSF sampling at Week 24)
 - Collect blood and urine for biomarker analyses
- Menstrual cycle questionnaire (for women of child-bearing potential)
- 12-Lead ECG
- Dispense IP to participant
- Perform IP compliance (remind of the importance of compliance, count number of unused sachets remaining in participant's supply from the previous in-clinic visit)
- Remind participant to bring any unused IP to the next visit

6.11.6 ATE Week 20 Telephone Visit

This visit will take place via telephone at 140 ± 3 days after the Week 24 Visit of the placebocontrolled portion of the trial. The following procedures will be performed:

- Administer ALSFRS-R questionnaire
- Review concomitant medications
- Assess and document AEs, including Key Study Events (see section 10.3 of Master Protocol)
- Perform IP compliance (remind of the importance of compliance)
- Remind participant to bring any unused IP to the next visit

6.11.7 ATE Week 24 Telephone Visit

This visit will take place via telephone at 168 ± 3 days after the Week 24 Visit of the placebocontrolled portion of the trial. The following procedures will be performed:

- Administer ALSFRS-R questionnaire
- Review concomitant medications
- Assess and document AEs, including Key Study Events (see section 10.3 of Master Protocol)
- Perform IP compliance (remind of the importance of compliance)
- Remind participant to bring any unused IP to the next visit

6.11.8 ATE Week 28 Visit

Participants should be instructed to hold investigational product on the day of the study visit. Investigational product should not be taken until after study visit procedures are complete.

The ATE Week 28 Visit will take place in-person 196 ± 14 days after the Week 24 Visit of the placebo-controlled portion of the trial. The following procedures will be performed:

- Collect vital signs including weight
- Perform SVC
- Muscle strength assessment
- Administer ALSFRS-R questionnaire
- ALSAQ-40
- CNS Bulbar Function Scale
- ROADS
- Review concomitant medications
- Assess and document AEs, including Key Study Events (see section 10.3 of Master Protocol)
- Administer the C-SSRS Since Last Visit questionnaire
- Collection of blood and urine samples [pre-dose]

- Collect blood samples for Clinical Safety Labs and, for WOCBP, for pregnancy test if applicable
- Hormone safety laboratory tests
- Plasma/serum for biomarker analyses
- Collect blood and urine for biomarker analyses
- Collect blood RNA
- Menstrual cycle questionnaire (for women of childbearing potential)
- 12-Lead ECG
- Lumbar puncture for CSF collection (optional)
 - Lumbar puncture may occur up to one week prior to the ATE Week 28 Visit.
- Dispense IP to participant
- Perform IP compliance (remind of the importance of compliance, count number of unused sachets remaining in participant's supply from the previous clinic visit)
- Remind participant to bring any unused IP to the next visit

6.11.9 ATE Week 40 Visit

Participants should be instructed to hold IP on the day of the study visit. Investigational product should not be taken until after study visit procedures are complete.

The ATE Week 40 Visit will take place in-person 280 ± 14 days after the Week 24 Visit of the placebo-controlled portion of the trial. The following procedures will be performed:

- Collect vital signs including weight
- Perform SVC
- Administer ALSFRS-R questionnaire
- CNS Bulbar Function Scale
- Review concomitant medications
- Assess and document AEs, including Key Study Events (see section 10.3 of Master Protocol)
- Administer the C-SSRS Since Last Visit questionnaire
- Collection of blood and urine samples [pre-dose]
 - Collect blood samples for Clinical Safety Labs and, for WOCBP, for pregnancy test if applicable
 - Coagulation laboratory tests
- Menstrual cycle questionnaire (for women of childbearing potential)
- 12-Lead ECG
- Dispense IP to participant
- Perform IP compliance (remind of the importance of compliance, count number of unused sachets remaining in participant's supply from the previous clinic visit)

• Remind participant to bring any unused IP to the next visit

6.11.10 ATE Week 52 Visit

Participants should be instructed to hold IP on the day of the study visit. Investigational product should not be taken until after study visit procedures are complete.

The ATE Week 52 Visit will take place in-person 364 ± 14 days after the Week 24 Visit of the placebo-controlled portion of the trial. The following procedures will be performed:

- Collect vital signs including weight
- Perform SVC
- Muscle strength assessment
- Administer ALSFRS-R questionnaire
- ALSAQ-40
- CNS Bulbar Function Scale
- ROADS
- Review concomitant medications
- Assess and document AEs, including Key Study Events (see section 10.3 of Master Protocol)
- Administer the C-SSRS Since Last Visit questionnaire
- Collection of blood and urine samples [pre-dose]
 - Collect blood samples for Clinical Safety Labs and, for WOCBP, for pregnancy test if applicable
 - Hormone safety laboratory tests
 - Plasma/serum for biomarker analyses
 - Collect blood and urine for biomarker analyses
 - Collect blood RNA
- Menstrual cycle questionnaire (for women of childbearing potential)
- 12-Lead ECG
- Lumbar puncture for CSF collection (optional)
 - Lumbar puncture may occur up to one week prior to the ATE Week 52 Visit.
- Perform IP compliance (remind of the importance of compliance, count number of unused sachets remaining in participant's supply from the previous clinic visit)
- Vital status determination

If the results of the placebo-controlled period are not available and a decision about future development has not been made:

• Dispense IP to participant; inform of next visit to occur in 12 weeks

6.11.11 Ongoing Extension Visit

For applicable participants who consent to continue in the ATE period after completing the assessments at ATE Week 52, the Ongoing Extension Visit will take place in-person approximately every 12 weeks (84 ± 7 days) thereafter, until the results of the placebo-controlled period of the study are available and a decision has been made about future development. At each of these visits, the following procedures will be performed:

- Collect vital signs including weight
- Administer ALSFRS-R questionnaire
- Review concomitant medications
- Assess and document AEs, including Key Study Events (see section 10.3 of Master Protocol)
- Administer the C-SSRS Since Last Visit questionnaire
- Collection of blood and urine samples [pre-dose]
 - Collect blood samples for Clinical Safety Labs and, for WOCBP, for pregnancy test if applicable
 - Hormone safety laboratory tests
- Menstrual cycle questionnaire (for women of childbearing potential)
- 12-Lead ECG
- Perform IP compliance (remind of the importance of compliance, count number of unused sachets remaining in participant's supply from the previous clinic visit)

If the results of the placebo-controlled period are not available and a decision about future development has not been made:

• Dispense IP to participant; inform of next visit to occur in 12 weeks

6.11.12 Follow-Up Safety Call in ATE

Participants will have a Follow-Up Safety Call 28 + 3 days after their last dose of IP.

The following procedures will be performed:

Assess and document AEs

6.11.13 Process for Early Terminations in ATE

Participants who withdraw consent or early terminate from the study and do not complete the protocol will be asked to be seen for an in-person Early Termination Visit and complete a Follow-Up Safety Call.

The in-person Early Termination Visit should be scheduled as soon as possible after a participant early terminates. If the participant early terminates or withdraws consent during the ATE period, all assessments that are collected at the ATE Week 52 in-clinic visit should be conducted. The Follow-Up Safety Call should be completed approximately 28 days after the last dose of investigational product.

If the Early Termination Visit occurs approximately 28 + 3 days after the last dose of investigational product, the information for the Follow-Up Safety Call can be collected during the Early Termination Visit, and a separate Follow-Up Safety Call does not need to be completed. If the in-person Early Termination Visit does not occur within 28 + 3 days of the last dose of investigational product, the Follow-Up Safety Call should occur approximately 28 days after the last dose of investigational product and the Early Termination Visit will be completed after the Follow-Up Safety Call.

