The maximum duration of the placebo-controlled treatment portion is 24 weeks. The duration of the Active Treatment Extension (ATE) period is planned for approximately 52 weeks from the first ATE visit of the final participant in Regimen F or until the primary results of the 24-week placebo-controlled period are available and a decision about further development has been made.

Follow-up Duration

At the conclusion of the 24-week placebo-controlled treatment period of the study, all participants will continue in the ATE period of the study. Any participant who stops study medication will have a 28-day follow up safety phone call and end their participation in the regimen. The duration of the ATE period is planned for approximately 52 weeks from the first ATE visit of the final participant in Regimen F.

Total Planned Trial Duration

Including the placebo-controlled treatment period and the integral ATE period, the total planned amount of time for a participant in the trial is a minimum of approximately 86 weeks. This duration assumes a 6-week screening window, 24-week placebo-controlled treatment period, a 52-week or longer ATE period, and a 4-week safety follow-up period.

SCHEDULE OF ACTIVITIES – PLACEBO CONTROLLED PERIOD

Activity (page 1 of 2)		Master Protocol Screening ¹	Regimen Specific Screening ¹	Baseline	Week	Week 4 ¹³	Week 8 ¹³	Week 12	Week 16 ¹³	Week 20	Week 24 or Early Term.	Follow-Up Safety Call ¹¹
	Master	Clinic	Clinic	Clinic	Phone	Clinic	Clinic	Phone	Clinic	Phone	Clinic	Phone
	Protocol or Regimen- Specific	-42 to -1 Days ¹⁵	-41 to 0 Days ¹⁵	Day 0	$\begin{array}{c} \text{Day} \\ 14 \pm 3 \end{array}$	Day 28 ±7	Day 56 ±7	Day 84 ±3	Day 112 ±7	Day 140 ±3	Day 168 ±7	28 days after last dose +3 days
Written Informed Consent ²	Master	X	X									
Inclusion/Exclusion Review	Master	X	X^3									
ALS & Medical History	Master	X										
Demographics	Master	X										
Physical Examination	Master	X										
Neurological Exam	Master	X										
Vital Signs ⁴	Master	X		X		Х	X		X		X	
Slow Vital Capacity	Master	X^{15}		X			X		X		X	
Muscle Strength Assessment	Master			X			X		X		X	
ALSFRS-R	Master	X		X		X	X	X	X	X	X	
ALSAQ-40	Regimen			X							X	
ROADS	Regimen			X			X		X		X	
CNS Bulbar Function Scale	Regimen			X			X		X		X	
12-Lead ECG	Regimen	X		X			X		X		X	
Clinical Safety Labs ^{5,16}	Master	Х		X		X	X		X		X	
Hormone Assessments ^{16,19}	Regimen		X			Х			X		X	
Menstrual Cycle Questionnaire 18	Regimen			X		X	X		X		X	

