12 Vital status, defined as a determination of date of death or PAV status or date last known alive, will be determined for each participant at the end of their follow-up (generally the Week 52 visit, as indicated). If at that time the participant is alive, his or her vital status should be determined again at the time of the last participant last visit (LPLV) of the regimen. We may also ascertain vital status (death or date last known alive only) at later time points by using publicly available data sources as described in section 8.15 of the Master Protocol.

13 When a participant completes the ATE Week 52 assessments, if the results of the placebo-controlled period of the trial are not available and a decision about further development has not been made, the participant will continue treatment for additional periods of approximately 12 weeks. In such a case, an Ongoing Extension Visit should be completed in the clinic every 12

HEALEY ALS Platform Trial Regimen-Specific Appendix F, ABBV-CLS-7262 Version 3.0, 07/23/2024 CONFIDENTIAL weeks $(84 \pm 7 \text{ days})$ until the results of the placebo-controlled period of the trial are available and a decision about further development has been made, or until discontinuation from the study.

14 Assessments collected during Week 24 visit in placebo-controlled phase are the same for the Baseline visit in the ATE phase 15 CSF collection is optional in the ATE. CSF may be collected up to one week prior to ATE Week 28 and ATE Week 52 Visits.

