2.3 Study Comparisons

- The primary comparison of interest is between the ABBV-CLS-7262 120 mg dose group and the shared concurrent placebo group when evaluating primary and secondary endpoints in the RCT data set.
- The primary comparison of interest in ATE is between ABBV-CLS-7262 120 mg RCT/ABBV-CLS-7262 120 mg ATE vs. placebo RCT/ABBV-CLS-7262 120 mg ATE based on combined RCT and ATE data sets.
- Comparisons involving the ABBV-CLS-7262 240 mg dose group and comparisons other than the primary comparison of interest are exploratory for both RCT and ATE data sets.
- Dose-dependent contrasts are of primary interest for pharmacokinetic endpoints in RCT.

Detailed comparisons will be defined in the R-SAP.

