6.10 Process for Early Terminations

Participants who early terminate from the study and do not complete the protocol will be asked to be seen for an in-person Early Termination Visit and complete a Follow-Up Safety Call.

The in-person Early Termination Visit should be scheduled as soon as possible after a participant decides to early terminate. If the participant early terminates during the placebo-controlled portion of the Regimen, all assessments that are collected at the Week 24 in-clinic visit should be conducted. The Follow-Up Safety Call should be completed approximately 28 days after the last dose of IP. If a participant is unable to be seen in-person, safety assessments and others that can be done remotely should be performed.

If the Early Termination Visit occurs approximately 28 + 3 days after the last dose of investigational product, the information for the Follow-Up Safety Call can be collected during the Early Termination Visit, and a separate Follow-Up Safety Call does not need to be completed. If the in-person Early Termination Visit does not occur within 28 + 3 days of the last dose of IP, the Follow-Up Safety Call should occur approximately 28 days after the last dose of IP and the Early Termination Visit completed after the Follow-Up Safety Call.

If a participant decides to discontinue IP, but will be followed under the Intent To Treat (ITT) principle, an in-person Early Termination Visit and Follow-Up Safety Call are not necessary. Participants who are followed under ITT are eligible to continue into the ATE portion of the study, but are not eligible to re-initiate IP.

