9.3 Regimen Specific Operating Characteristics

Clinical trial simulations customized for Regimen F (ABBV-CLS-7262) are provided in Appendix I to the R-SAP. The primary comparison of the anchor dose (120 mg) to placebo control is powered at approximately 80% to detect a 30% slowing in disease progression (common to mortality and function decline). The type I error of the regimen is 2.5% assuming no systematic differences in rates of progression across regimens contributing to the concurrent controls. More details are provided in Appendix I to the R-SAP.

[figure not shown]
Given the sample size of 165 participants on 120 mg (RCT treatment)/120 mg (ATE treatment) and 75 participants on placebo (RCT treatment)/120 mg (ATE treatment), the study will also have approximately 85% power on the CAFS at ATE Week 52, and approximately 80% power for survival through to the end of the ATE period. Such calculations were performed with assumptions for an 18-month survival rate of 70% for placebo RCT/120 mg ATE group and an 86% survival rate for 120 mg RCT /120 mg ATE group at ATE Week 52, with a 12-month accrual period (totaling a maximum study duration of 30 months) and 13% drop-out rate due to non-mortality reasons. The treatment difference for change from baseline in ALSFRS-R total score was assumed 20% slowing of disease progression rate versus delayed initiation of ABBV-CLS-7262 with a standard deviation of 9.0 at ATE Week 52 (accounting for a partial cross-over effect). An exponential distribution was assumed for power assessment of CAFS and survival endpoints. These tests for power analysis were done with a two-sided significance level of 0.05.

[figure not shown]

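### The protocol contradicts itself on whether a participant who stops drug stays in follow-up, which puts later functional data in the primary ATE comparison at risk of differential loss

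*Protocol*

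**What the plan says.** Three places in the protocol deal with a participant who stops drug.

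- **Regimen-Specific Appendix Summary, Follow-up Duration:** "Any participant who stops study medication will have a 28-day follow up safety phone call and end their participation in the regimen". The sentence comes directly after the statement that everyone continues into the ATE, but it names no period.
- **Section 6.10 (placebo-controlled period):** its last paragraph lets a participant discontinue drug and still be followed under the intention-to-treat (ITT) principle, without an Early Termination Visit or safety call. It adds: "Participants who are followed under ITT are eligible to continue into the ATE portion of the study, but are not eligible to re-initiate IP".
- **Section 6.11.13 (ATE):** "Participants who withdraw consent or early terminate from the study and do not complete the protocol will be asked to be seen" at an Early Termination Visit, where "all assessments that are collected at the ATE Week 52 in-clinic visit should be conducted". The section otherwise follows 6.10 closely but has no ITT paragraph.

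The ATE Schedule of Activities, footnote 12, determines vital status at the end of each participant's follow-up. If the participant is then alive, "his or her vital status should be determined again at the time of the last participant last visit (LPLV) of the regimen".

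Section 2.3 names the primary ATE comparison: "ABBV-CLS-7262 120 mg RCT/ABBV-CLS-7262 120 mg ATE vs. placebo RCT/ABBV-CLS-7262 120 mg ATE based on combined RCT and ATE data sets". Section 2.2 lists its efficacy endpoints: CAFS, ALSFRS-R, SVC and the ALSAQ-40 ADL score at ATE Week 52, and survival to the end of the ATE.

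**The concern.** The two arms of the ATE comparison meet 120 mg at different times. The early-start arm's first 24 weeks on drug fall in the placebo-controlled period, where section 6.10 offers follow-up off drug. The delayed-start arm's first 24 weeks on drug fall in the ATE, where no such route is given and the Summary says participation ends. Two participants who stop at the same early exposure can therefore leave different amounts of data, depending on the arm to which they were randomized.

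At stake are ALSFRS-R, SVC, ALSAQ-40 ADL and the functional part of CAFS at ATE Week 52. If those who stop differ in progression from those who stay, and are missing in different proportions in the two arms, the functional comparison can shift. Functional data not collected at the time cannot be recovered later.

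**Working it through.** **1. The plan's own power figures.** Section 9.3 states about 80% power for survival and about 85% for CAFS. Its inputs are 165 early-start and 75 delayed-start participants, survival of 86% and 70% at 18 months, a single 13% non-mortality dropout figure not split by arm, exponential distributions, and two-sided 0.05.

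- Hazard ratio = ln(0.86)/ln(0.70) = 0.423; |ln HR| = 0.861.
- Monthly rates: delayed -ln(0.70)/18 = 0.01982; early -ln(0.86)/18 = 0.00838; dropout -ln(0.87)/18 = 0.00774.
- Expected events = n × λ/(λ+η) × [1 - exp(-18(λ+η))]. Delayed: 75 × 0.719 × 0.391 = 21.1. Early: 165 × 0.520 × 0.252 = 21.6. Total 42.7.
- Power = Φ(0.861/√(1/21.1 + 1/21.6) - 1.96) = 0.80. A simulated log-rank test also gives 0.80.

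The survival figure reproduces with fixed 18-month follow-up. With no non-mortality loss at all, the same formula gives 0.83, so this loss costs survival power little. The CAFS figure cannot be reproduced exactly, because the control ALSFRS-R decline is not stated. A rank-test simulation that excludes dropouts gives 0.82 at an assumed 0.6 points per month and 0.87 at 0.7.

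**2. Which text applies to a stop.**

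| Stop occurs | Early start | Delayed start |
|---|---|---|
| Placebo-controlled period | 6.10 (on 120 mg) | 6.10 (on placebo) |
| ATE | 6.11.13 (after 24 weeks or more on 120 mg) | 6.11.13 (includes first exposure to 120 mg) |

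By calendar period the rows are the same in both arms. By drug exposure they are not: section 6.10 covers 24 of the early-start arm's 24 + 52 = 76 planned weeks on drug, including all of first exposure, and 0 of the delayed-start arm's 52. The Summary sentence, taken literally, contradicts 6.10 in the first row and is the only explicit statement on a drug stop in the second.

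**3. What is not collected.** Sections 6.11.2 to 6.11.10 schedule ALSFRS-R at ATE Weeks 4, 8, 12, 16, 20, 24, 28, 40 and 52 (9 occasions) and SVC at Weeks 4, 8, 16, 28, 40 and 52 (6). Suppose a participant stops drug and has the Early Termination Visit near ATE Week 8. ALSFRS-R is then not collected on 7 of 9 occasions (Weeks 12 to 52), nor SVC on 4 of 6 (Weeks 16 to 52). The visit includes an ALSAQ-40, but not one at Week 28 or 52.

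**4. How far the functional comparison could move.** Let q be the share unobserved at ATE Week 52 and gap = mean(unobserved) - mean(observed). The true arm mean is the observed mean + q × gap, so each arm's error is -q × gap. With a common gap:

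bias in (early - delayed) = (q_delayed - q_early) × gap.

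The documents give neither q by arm nor the gap. All values below are assumptions.

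| q delayed | q early | gap -6 | gap 0 | gap +6 |
|---|---|---|---|---|
| 0.10 | 0.10 | 0 | 0 | 0 |
| 0.10 | 0.05 | -0.3 | 0 | +0.3 |
| 0.15 | 0.05 | -0.6 | 0 | +0.6 |
| 0.20 | 0.05 | -0.9 | 0 | +0.9 |

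The extreme, 0.9 points, is 0.9/9.0 = 0.1 of the standard deviation assumed in section 9.3.

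**The case against.** A reader might infer that delayed-start participants who stop 120 mg are lost while early-start participants who stop are followed, so that the ATE comparison is biased. The documents do not support that.

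- **Not lost.** ATE early terminators are asked for a visit with the full ATE Week 52 assessments, and vital status is rechecked at the regimen's last participant last visit. Survival and the survival part of CAFS are largely protected.
- **Not assuredly followed.** Follow-up under 6.10 is optional, and the Summary contradicts it.
- **Same text at the same time.** At any given time since randomization both arms face the same rule. Early-start participants who stop in the ATE meet the same gap, and placebo participants who stop earlier are covered by 6.10. The difference is confined to stops in the first 24 weeks on drug.
- **Bias not shown.** Its sign depends on whether those who stop progress faster or slower, and it vanishes if the shares or the outcomes match. No ATE estimand or missing-data method can be judged: section 1 of the R-SAP limits that plan to the placebo-controlled period.

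All four points stand.

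A fifth is that 6.11.13 is merely silent: it addresses leaving the study, not stopping drug, and the Master Protocol, not among these documents, may hold a general ITT rule. This stands only in part. The Summary goes beyond silence by ending participation. On non-analysis matters, the table in R-SAP section 1 ranks the Regimen-Specific Appendix above the Master Protocol (5 against 4), so a general rule there would still conflict with the Summary and be outranked.

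**Conclusion.** The conflict is real and rests on the text alone. The Summary ends participation on stopping drug, 6.10 allows follow-up off drug into the ATE, and 6.11.13 provides no such route for a stop during the ATE. Followed as written, the protocol forgoes functional data after the Early Termination Visit for participants who stop in the ATE, and it treats stops at early exposure differently in the two arms.

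The consequence is a risk of differential missing functional data, not a demonstrated bias. The range of -0.9 to +0.9 ALSFRS-R points assumes 10 to 20% unobserved in the delayed-start arm, 5% in the early-start arm and a common gap of -6 to +6 points. It illustrates scale and is not an estimate. The Week 24 primary analysis and the R-SAP's secondary testing sequence are unaffected, because all their endpoints are at Week 24. The point is worth correcting because the ATE comparison is named as primary for that period and the remedy is small.

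**What to change.** Reconcile the three places so that each period has one statement on whether stopping drug ends follow-up:

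- In the Summary, limit the sentence on stopping study medication to participants who leave the study.
- In 6.11.13, add that a participant who discontinues drug during the ATE may remain in follow-up under ITT, with the scheduled ATE efficacy assessments through ATE Week 52. At a minimum, keep ALSFRS-R by telephone, which is already done at ATE Weeks 12, 20 and 24. Vital status is already planned.
- In the ATE analysis plan, state the estimand and how data after drug discontinuation are used.

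The cost is a short protocol edit and some additional visits or calls, all on the existing schedule, for what should be a small number of off-drug participants. It is not zero: SVC generally means a clinic visit for someone who might otherwise have left, which is why the telephone option is the fallback. Section 6.10 already places off-drug participants in the ATE, so this extends an existing policy. The change concerns data collection only and alters no dosing or stopping rule.
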